#### 9.5. Subject Status and Classification

As subjects are evaluated, enrolled and treated in the study, they will be grouped into one of the following several categories. Categorization will help determine how data gathered from them will be stored and evaluated.

It is the investigational sites's responsibility to list all screened subjects, Consent Ineligible (Screening failure), Intent, Attempt and TREATMENT subjects on the Screening and Enrollment Log.

#### 9.5.1. Consent Ineligible (Screening Failure):

A subject who has signed informed consent but is later determined to not meet eligibility criteria will be classified as "Consent Ineligible". Subjects not meeting eligibility criteria due to oversight (i.e. I/E violation) will be considered 'consent ineligible' but will also be required to enter a protocol deviation. There are no follow-up reporting requirements for consent ineligible subjects. Subjects determined to be Consent Ineligible will not be used for analysis of the endpoints. The original signed Informed Consent must be maintained in the site's subject file. A subject Identification Number (ID) will be assigned in the EDC system.

For consent ineligible subjects the following forms must be completed:

- Enrollment and End of Study eCRF must be completed
  - Relevant CRFs for study visits completed through consent ineligible determination, including device tracking, if applicable.
- Adverse Event forms for any reportable event, as defined in Section 18.1 for any adverse event that occurs after signing the Informed Consent, up to the point of subject withdrawal

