Enapoints	
 
Secondary Safety Endpoint – SAE and AE Rates
 
Secondary Effectiveness Endpoint 1 – New or Increased Dose of AAD
 
				
	
 
Secondary Effectiveness Endpoint 2 – Single Procedure Success defined as freedom from primary effectiveness failure without a repeat procedure
 
Secondary Effectiveness Endpoint 3 – Symptomatic Recurrence: freedom from documented symptomatic AF/AT/AFL recurrence
 
				
Additional	Other additional endpoints and analysis include, but are not limited to:				
Endpoints	
 
Changes in the quality of life measures (AFEQT and EQ-5D-5L) between baseline and 12 months follow up
 
				
	
 
Total RF time for the index procedure (defined as the summation of all RF application durations)
 
				
	Total number of RF applications				
	
 
Total fluoroscopy time for the index procedure
 
				

Cli n ical E valu	nation of the StablePoint Catheter and Force-Sensing System for Paroxysmal Atrial Fibrillation
	(NEWTON AF)
	
 
Total index procedure time
 
Freedom from recurrence of individual types of atrial arrhythmias between 91 and 365 days from index procedure: 1) AF 2) AT 3) AFL
 
Freedom from cardiovascular hospitalization at 12 months
 
Quantification of parameters used during RF Application including RF power, RF duration, contact force and Local Impedance via DIRECTSENSE™ technology
 
Descriptive summaries of primary safety and effectiveness endpoints at 12 months using the data available at the time of the 6-month analysis
 
The predicted probability of success for the primary effectiveness endpoint at 12 months based off the data available at the time of the 6-month analysis.
 

Method of Assigning Subjects to Treatment	Any subject that signs the consent form, meets eligibility criteria, has the study device inserted into the body and receives ablation therapy will be assigned to the TREATMENT group.
Follow-up Schedule	Subjects will complete a pre-discharge visit, 1-month, 3-month, 6-month, and 12-month visit.
Study Duration	Enrollment is expected to be completed in approximately 12 months; therefore, the total study duration is estimated to be approximately 24 months.
Participant Duration	The study duration for each subject is expected to be approximately 12 months.

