# 7. Study Design

The NEwTON AF study is a multi-center, global, prospective, single arm study to establish the safety and effectiveness of the IntellaNav StablePoint Catheter and Force-Sensing System in subjects with symptomatic, drug refractory, recurrent paroxysmal atrial fibrillation. The study will be conducted in North America, Europe and Asia Pacific. A 6-month endpoint analysis is planned and will be conducted after all 299 TREATMENT subjects have completed 30 days of follow up and 183 TREATMENT subjects have completed their 6-month follow-up. All subjects undergoing the index procedure with the study devices will be followed up to 12 months.

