#### 9.5.3. **Attempt**

An attempt subject is one who signs informed consent, meets eligibility criteria, and has any study device inserted into the body but does not receive ablation (RF energy) with the StablePoint Catheter System. Attempt subjects will be used for analysis of the primary safety endpoints and additional analyses of safety data, but attempt subjects will not be used for analysis of the primary effectiveness endpoints or additional analyses of effectiveness data (additional analysis include subgroup, multivariable, and center pooling analyses). Attempt subjects do not count toward the enrollment ceiling.

The original signed Informed Consent and any relevant documentation must be maintained in the site's subject file. A subject ID will be assigned in the EDC system. Attempt subjects are not allowed to be re-enrolled in the study.

Attempt subjects will be followed up to 30 days for safety. Subjects will not need to complete post-procedure arrythmia monitoring as these subjects will not count toward the analysis of the effectiveness endpoints. All applicable case report forms, per the protocol, will be completed.

For attempt subjects, at the miniumum the following forms must be completed:

- Enrollment and baseline forms such as, but not limited to: informed consent, enrollment information and other related forms;
- End of Study form;
- Protocol Deviation form
- Adverse Event forms for any reportable event, as defined in Section 18.1 for any adverse event that occurs after signing the Informed Consent, up to the point of subject withdrawal

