#### 9.5.4. Treatment

Any subject that signs the consent form, meets eligibility criteria and has the specified study device inserted into the body and receives RF ablation with the StablePoint Catheter System will be classified as "TREATMENT". These subjects are followed in accordance with the follow-up schedule and are included in all study analyses. A subject ID will be assigned in the EDC system.

All applicable case report forms, per the protocol, must be completed for TREATMENT subjects. TREATMENT subjects do count towards the enrollment ceiling and will be used for analyses of the endpoints. The original signed Informed Consent and any relevant documentation must be maintained in the center's patient file.

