#### 11.3. General Statistical Methods

### 11.3.1. Analysis Sets

While each endpoint was individually powered, each safety endpoint analysis will use all available data from all ATTEMPT and TREATMENT subjects, and each effectiveness endpoint analysis will use all available data from all TREATMENT subjects.

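### The Consent Ineligible class has no cut-off in time, so a subject exposed to the study catheter and later found ineligible drops out of every primary analysis set

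*Combined protocol and SAP*

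**What the plan says.** Section 9.5.1 classes as Consent Ineligible any consented subject later found not to meet the criteria. It extends this to missed violations: "Subjects not meeting eligibility criteria due to oversight (i.e. I/E violation) will be considered 'consent ineligible", with a protocol deviation also to be entered. Two consequences follow: "Subjects determined to be Consent Ineligible will not be used for analysis of the endpoints" and "There are no follow-up reporting requirements for consent ineligible subjects". Adverse event forms are required only up to withdrawal. Device tracking is among the forms listed for the class, where applicable, so device use within it is foreseen.

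The other classes are conditional on eligibility:

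- Synopsis, row on how the treatment group is assigned: "Any subject that signs the consent form, meets eligibility criteria, has the study device inserted into the body and receives ablation therapy".
- Section 9.5.3: "An attempt subject is one who signs informed consent, meets eligibility criteria, and has any study device inserted into the body".
- Section 9.5.4: "Any subject that signs the consent form, meets eligibility criteria and has the specified study device inserted into the body and receives RF ablation".
- The definitions of both classes in Section 26.2 carry the same condition.

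Under Section 11.3.1, "each safety endpoint analysis will use all available data from all ATTEMPT and TREATMENT subjects", and the effectiveness analyses use TREATMENT subjects only.

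On follow-up, the synopsis and Section 7 both state: "All subjects undergoing the index procedure with the study devices will be followed up to 12 months".

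**The concern.** Take a subject who receives RF and whose exclusion criterion is noticed a month later, for example when a monitor reads the source documents. Section 9.5.1 makes this subject Consent Ineligible. Sections 9.5.3 and 9.5.4 do not admit the subject, and Section 11.3.1 has no other route into an analysis set. Events before withdrawal are recorded and go to the Clinical Events Committee and the Data Monitoring Committee (Sections 21.2 and 21.3), but they do not count in the safety endpoints.

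The trial is open, has one arm and is judged against fixed performance goals, so membership of the analysis set is one of its main protections against bias. If a closer look at eligibility is prompted by a complication or a recurrence, the subjects removed will tend to be those with events, and the result will favour the device. The documents do not show that this happens. The defect is that the rule permits it.

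**Working it through.** **1. What each place settles.**

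| Place | What it settles | Covers a violation found after RF? |
|---|---|---|
| 9.1, 10.3 | Final eligibility check before RF; ineligibility found before RF is documented | No |
| Table 10-1 | Eligibility reviewed at enrollment, baseline and index procedure | No |
| 10.6.2 | ICE at the start of the procedure may decide eligibility | No |
| Exclusion-criteria footnote, 10.5.1 | Thrombus found: Consent Ineligible | No, pre-ablation |
| 9.5.1 | Oversight violations: Consent Ineligible, no time limit | Yes, and it excludes |

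Only Section 9.5.1 classifies the late-found case.

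**2. The plan's own figure.** Section 11.1.4.2 (12-month safety) gives an expected rate of 94%, a goal of 89%, one-sided 2.5%, power 80%, attrition 10% and N = 299.

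n = [1.960·√(0.89·0.11) + 0.842·√(0.94·0.06)]² / 0.05² = 265 after rounding up; 264.5/0.90 = 294. This is within 2% of 299, so the stated size is not in dispute.

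**3. Pass/fail boundary.** Simplifications: no censoring, ATTEMPT subjects ignored. With S = 1 − x/n, the log-log lower limit is S^exp(z·se), where se = √[x/(n(n−x))]/|ln S|.

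Example, 30 days, 21/299: S = 0.9298, se = 0.2183, z = 1.645, limit = 0.9010.

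| Endpoint and limit | Last pass | First fail | First fail with one event-bearing subject dropped |
|---|---|---|---|
| 30 days, 95%, goal 90% (11.1.1.3) | 21/299: 0.9010 | 22/299: 0.8971 | 21/298: 0.9006, pass |
| 12 months, 97.5%, goal 89% (11.1.4.3) | 22/299: 0.8904 | 23/299: 0.8865 | 22/298: 0.89004, pass |
| 12 months, 95%, goal 89% (synopsis) | 23/299: 0.8933 | 24/299: 0.8895 | 23/298: 0.8930, pass |

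The last row is shown because the synopsis states a 95% limit at 12 months where Section 11.1.4.3 states 97.5%. That is a separate inconsistency.

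**4. Type I error if one event-bearing subject is dropped in every trial.** The allowed count rises by one, so the exact binomial tail at the goal gives:

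- 30 days, p = 0.10: P(X ≤ 21) = 0.048 becomes P(X ≤ 22) = 0.072.
- 12 months, p = 0.11, 97.5% limit: P(X ≤ 22) = 0.023 becomes P(X ≤ 23) = 0.037.
- 12 months, 95% limit: P(X ≤ 23) = 0.037 becomes P(X ≤ 24) = 0.056.

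**5. The same with planned attrition** (5% per year at 30 days, 10% at 12 months). This used 20,000 simulated Kaplan-Meier trials with exponential dropout. Event timing is assumed: days 0 to 7, with 1/11 of the 12-month events spread over days 30 to 365.

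- 30 days: 0.048 to 0.073.
- 12 months, 97.5%: 0.018 to 0.025.
- 12 months, 95%: 0.040 to 0.061.

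**6. By share reclassified.** The documents give no expected number of violations, so the share v is assumed. Events E ~ Bin(299, p); dropped events K ~ Bin(E, v); event-free subjects are dropped either never or at the same rate v. No censoring.

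| v | 30 days, events only | 12 months (97.5%), events only | 30 days, unrelated to outcome | 12 months (97.5%), unrelated |
|---|---|---|---|---|
| 1% | 0.053 | 0.026 | 0.042 | 0.018 |
| 2% | 0.059 | 0.028 | 0.039 | 0.018 |
| 5% | 0.077 | 0.036 | 0.043 | 0.018 |

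Inflation appears only when reclassification is related to outcome.

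**7. Effectiveness.** At 12 months (97.5% limit, goal 50%), 132/299 passes with a limit of 0.5003. Restoring one excluded subject with an event gives 133/300 and 0.4986, a fail. No type I error was calculated for effectiveness.

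**The case against.** The best reply is that the class was meant for findings before treatment. It is headed as screening failure, eligibility is scheduled for review only up to the index procedure, Sections 9.1 and 10.3 require the final check before RF, and the thrombus examples are pre-ablation. A narrower intent is likely. But those sections time the check; they do not say what becomes of a subject in whom it failed. Section 9.5.1 does say, and it excludes.

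The follow-up conflict can be called a missing cross-reference, since the 12-month sentence is a general summary and ATTEMPT subjects already depart from it with 30 days (Sections 7.1, 9.5.3 and 10.9). That holds for subjects without RF. For a subject who received RF, the two statements cannot both be followed.

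On size, several criticisms stand. Dropping one event-bearing subject in every trial is a strong assumption: with 299 × 0.10 = 29.9 expected events at the 30-day goal, it is about 3.3% of them. The 12-month shift without censoring rests on 22/298 passing by 0.00004, and with planned attrition the 97.5% result reaches only 0.025, which is nominal. At 1% the effect is small.

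Selective removal would also leave a trace: many criteria are dated baseline facts, an oversight case needs a deviation with reason and date (Section 14), and related events are adjudicated. This makes misuse auditable but does not return the subject to the endpoint.

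Finally, Sections 11.4.5 and 11.4.6 refer to a separate Statistical Analysis Plan that is not among the documents. It might treat such subjects differently, but it would then contradict Section 9.5.1.

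**Conclusion.** The concern holds. On the text, a subject exposed to the catheter or to RF and found ineligible afterwards belongs to no primary analysis set, and for a subject who received RF the follow-up rules contradict each other.

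The effect on error rates is conditional. If reclassification is confined to subjects with events, at an assumed 1% to 5% of them and without censoring, the 30-day type I error is 0.053 to 0.077 against a nominal 0.05, and the 12-month error (97.5% limit) is 0.026 to 0.036 against 0.025. If it is unrelated to outcome, both stay below nominal. The number of violations is not known, and there is no evidence of selective use. This should be fixed before the analysis because the rule permits bias in one direction and is cheap to close.

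**What to change.** - In Section 9.5.1, limit Consent Ineligible to subjects found ineligible before any study device (StablePoint) is inserted.
- Remove the eligibility condition from the ATTEMPT and TREATMENT definitions in the synopsis and in Sections 9.5.3, 9.5.4 and 26.2, so that exposure alone decides the class. A change to Section 9.5.1 alone would leave these subjects unclassified.
- Record violations found later as protocol deviations, keep the subjects in the Section 11.3.1 sets, and exclude them only in a named sensitivity analysis.
- Reconcile Section 9.5.1 with the synopsis and Section 7 on follow-up.
- Align the thrombus footnotes to the exclusion criteria and Sections 9.1 and 10.5.1. Thrombus found before the StablePoint catheter is inserted can remain Consent Ineligible. State the class once the catheter is in but no RF has been given; classification by exposure makes it ATTEMPT.

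The cost is wording in these sections, a few more subjects followed and analysed, and possibly slightly less favourable rates. The sample size does not change.

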#### 9.5.2. Intent

A subject who signs informed consent, meets eligibility criteria, but does not have any study devices inserted into the body will be classified as "INTENT." Subjects that are enrolled in the study but do not undergo ablation procedure within 30 days from consent signature date must not be reconsented and will be withdrawn from the study and classified as "INTENT." These subjects won't be allowed to be re-enrolled in the study.

There are no Follow Up requirements for Intent subjects. Intent subjects will not count for analysis of the endpoints. The original signed Informed Consent must be maintained in the center's patient file. A subject ID will be assigned in the EDC system.

For intent subjects, at the miniumum the following forms must be completed:

- Enrollment and baseline forms such as, but not limited to: informed consent, enrollment information and other related forms;
- End of Study form;
- Adverse Event forms for any reportable event, as defined in Section 18.1 for any adverse event that occurs after signing the Informed Consent, up to the point of subject withdrawal

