#### 10.6.2.1. Three-dimensional electroanatomical mapping

Prior to the ablation procedure a 3D electro-anatomical map of the left atrium is required for this study. The Rhythmia HDx™ mapping system and IntellaMap Orion mapping catheter must be used, and mapping acquisition times will be collected. A quality 3D electro-anatomical map is important to help visualize the pulmonary veins. The IntellaNav StablePoint catheter may be used to add supplemental geometry to the map at the Investigator's discretion.

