# Respiratory arrest/distress/insufficiency/dyspnea

- Arrhythmia (new or exacerbated)
- Conduction pathway injury (Complete heart block (transient or permanent), nodal injury, etc.)
- Nerve injury, for example:
  - o Phrenic nerve injury
  - Vagal nerve injury
- Gastrointestinal disorders
- Vessel trauma, including:
  - Perforation
  - Dissection
  - Coronary artery injury
  - Vasospasm
  - Occlusion
  - Hemothorax
- Cardiac trauma, for example:
  - Cardiac perforation/cardiac tamponade/pericardial effusion
  - Valvular damage
  - Stiff left atrial syndrome
- Injury related to tissue damage and/or adjacent structures and/or related structures, for example:
  - Esophageal injury
  - Physical trauma
  - Pulmonary injury
  - Catheter Entrapment
- Fistula, for example:
  - Atrio-esophageal fistula
  - Bronchopericardial fistula
- PV stenosis and its symptoms, for example:
  - o Cough
  - Shortness of breath,
  - o Fatigue
  - Hemoptysis
- Surgical and access complications, for example:
  - Hematoma/seroma
  - o AV fistula
  - o Bleeding

- Pseudoaneurysm
- Pneumothorax
- o Residual atrial septal defect

Injury due to embolism/thromboembolism/air embolism/foreign body embolism

- Cerebrovascular Accident (CVA)/stroke
- Transient Ischemia Attack (TIA)
- Myocardial infarction
- Neurological impairment and its symptoms, for example:
  - Cognitive changes, visual disturbances, headache, motor impairment, sensory impairment, and speech impairment
- Pulmonary embolism
- Asymptomatic cerebral embolism

The potential adverse events may be related to the diagnostic mapping catheter(s) and/or the interventional ablation device(s) and/or the procedure. The severity and/or the frequency of these potential adverse events may vary and may result in prolonged procedure time and/or additional medical and/or surgical intervention, implantation or permanent device such as a pacemaker, and in rare cases, may result in death. Refer to the RF Controller, Irrigation Pump, and other ancillary device instructions for additional potential adverse events related to their use with the IntellaNay StablePoint.

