Intent Subject	Any subject that signs the consent form but does not have any study devices inserted into the body. Subjects who are enrolled in the study but do not undergo ablation procedure within 30 days from consent signature date may not be reconsented and will be withdrawn from the study.		
In-patient Hospitalization	Hospitalizations ≥24 hours in duration or <24 hours with medical intravenous therapy or surgical intervention		
Index procedure time	Time from first sheath into last catheter removal		

Term	Definition		
LA dwell time	Time from StablePoint Catheter exiting the sheath in the LA to final PVI		
Myocardial infarction (in the context of AF ablation)	The presence of any one of the following criteria:  (1) detection of ECG changes indicative of new ischemia (new STT wave changes or new LBBB) that persist for more than 1 hour;  (2) development of new pathological Q waves on an ECG;  (3) imaging evidence of new loss of viable myocardium or new regional wall motion abnormality		
Paroxysmal Atrial Fibrillation (PAF)	Recurrent symptomatic Atrial Fibrillation that terminates spontaneously o with intervention within seven days of onset.		
Pericarditis	Inflammation of the pericardium surrounding the heart. Pericarditis should be considered a major complication following ablation if it results in an effusion that leads to hemodynamic compromise or requires pericardiocentesis, prolongs hospitalization by more than 48 hours, requires hospitalization, or persists for more than 30 days following the ablation procedure.		
Phrenic Nerve Palsy	Phrenic nerve palsy is defined as absent phrenic nerve function demonstrated radiographically. A phrenic nerve palsy is considered to be permanent when it is documented to be present 12 months or longer following ablation.		
Pneumothorax	Collapse of the lung due to an abrupt change in the intrapleural pressure		

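### A serious complication that stops the index procedure before StablePoint is inserted makes the subject INTENT, so the event is reported but enters neither primary safety endpoint

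*Combined protocol and SAP*

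**What the plan says.** **Classification.** Under section 9.5.2, a consented, eligible subject who "does not have any study devices inserted into the body will be classified as" INTENT. The same section states: "Intent subjects will not count for analysis of the endpoints" and "There are no Follow Up requirements for Intent subjects". A subject not ablated within 30 days of consent is withdrawn as INTENT and cannot be re-enrolled. Section 9.5.3 and Table 26-2 make insertion of a study device a condition for ATTEMPT.

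**Safety analysis set.** Section 11.3.1 says that "each safety endpoint analysis will use all available data from all ATTEMPT and TREATMENT subjects". INTENT subjects are not in it.

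**What a study device is.** The synopsis lists the test devices as the StablePoint catheter, cable, connection box and software module. Only the catheter enters the body. Orion appears under section 5.2, Additional Commercial Systems, at 5.2.7.

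**What happens before StablePoint is needed.** Section 5.2.7 makes Orion mandatory. Section 10.6.2.1 states: "Prior to the ablation procedure a 3D electro-anatomical map of the left atrium is required for this study". Section 10.5.2 begins the study-related ablation procedure at transseptal access. Table 26-2 defines index procedure time as "Time from first sheath into last catheter removal".

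**What the endpoints count.** Sections 6.1 and 6.4 count serious events related to the procedure as well as the device. They include tamponade/perforation, stroke, TIA and major vascular access complications. Section 18.1 adds: "The potential adverse events may be related to the diagnostic mapping catheter(s) and/or the interventional ablation device(s) and/or the procedure".

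**The concern.** The endpoint definition and the analysis set start at different points. The composite is written to capture complications of the procedure, and the documents place transseptal access inside the procedure. The analysis set opens only when StablePoint goes in.

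A tamponade from transseptal puncture or mapping that stops the case before insertion is therefore lost to the endpoint. The same tamponade counts if StablePoint is already in the body. Subjects leave the set because they had the outcome, so the omission cannot average out: each omitted subject of this kind carries an event and none carries a success. At stake are the comparisons with the 90% goal at 30 days and the 89% goal at 12 months, both of which are conditions of overall study success (6.6.2).

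**Working it through.** **1. Does the text lead there?** Take an eligible subject with a sheath in place, transseptal puncture done and Orion mapping under way, in whom a serious complication stops the case.
- No StablePoint component is in the body, so the subject is INTENT under 9.5.2 and cannot be ATTEMPT under 9.5.3.
- 11.3.1 admits only ATTEMPT and TREATMENT, so the event is in neither safety analysis.
- "Study device" has no entry of its own in Table 26-2. Section 19.5 glosses the study devices as the StablePoint ablation catheter, and 10.6.2.8 records the StablePoint system separately from non-study devices. Both support reading Orion as outside the term.

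**2. The plan's own sample sizes.** One-sample normal approximation, then inflation for attrition:

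n = [(z(1−α)·√(p0·q0) + z(power)·√(p1·q1)) / (p1 − p0)]²

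- 30 days (11.1.1.2: 95% against 90%, one-sided 5%, power 90%, attrition 5%): [(1.645×0.3000 + 1.282×0.2179)/0.05]² = 238.9, and 238.9/0.95 gives 252. The plan states 252.
- 12 months (11.1.4.2: 94% against 89%, one-sided 2.5%, power 80%, attrition 10%): [(1.960×0.3129 + 0.842×0.2375)/0.05]² = 264.5, and 264.5/0.90 gives 294. The plan states 299, which is within 2%.

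These figures are not in dispute.

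**3. Pass limits.** Inputs: 299 analysed subjects, no censoring, x events, S = 1 − x/n, and the log-log lower limit S^exp(z·se) with se = √[x/(n(n−x))]/|ln S|. For 30 days at x = 21: S = 0.9298, se = 0.01589/0.07282 = 0.2183, and the limit is 0.9298^exp(1.645×0.2183) = 0.9010.

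| Test | Passes | Fails | One omitted event added back |
|---|---|---|---|
| 30 days, 95% limit, goal 90% | 21/299: 90.10% | 22/299: 89.71% | 22/300: 89.75%, fails |
| 12 months, 97.5% limit, goal 89% | 22/299: 89.04% | 23/299: 88.65% | 23/300: 88.69%, fails |

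The 12-month row uses the 97.5% limit of 11.1.4.3. The synopsis gives a 95% limit for both safety endpoints.

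**4. Effect on a false pass.** Let q be the share of started procedures with a pre-insertion event that drops the subject. The documents give no value for q, so the range is an assumption. Set the true event rate among all started procedures exactly at the goal, r = 10% or 11%. The event rate in the analysed set is then (r − q)/(1 − q). For q = 0.5% at 30 days this is (0.10 − 0.005)/0.995 = 0.0955. The pass probability is P(X ≤ 21) at 30 days or P(X ≤ 22) at 12 months, with X binomial on 299.

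| q (assumed) | 30 days | 12 months |
|---|---|---|
| 0 | 4.8% | 2.3% |
| 0.1% | 5.3% | 2.6% |
| 0.3% | 6.4% | 3.2% |
| 0.5% | 7.8% | 3.9% |
| 1.0% | 12.4% | 6.5% |

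Under these assumptions even 0.1% takes both tests slightly above their nominal 5% and 2.5%.

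**5. At the expected rate.** If the true 30-day event rate is the planned 5%, the pass probability is 95.3% with nothing dropped and 97.3% at q = 0.3%. The rule then changes little.

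**The case against.** **Safety information is kept.** A reader might infer that these events vanish. They do not. Section 9.5.2 requires adverse event forms "for any adverse event that occurs after signing the Informed Consent, up to the point of subject withdrawal". Section 19.1 makes all serious and all procedure-related events reportable. On withdrawal at the investigator's discretion, 9.3 requires open reportable events to be followed until closed or chronic. Section 21.2 sends procedure-related events to the Clinical Events Committee, whose dossier may show an intent classification, and 21.3 gives the Data Monitoring Committee oversight of all adverse events. All of this stands. The gap lies in the primary estimate and not in surveillance.

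**The pathway is narrow.** A reader might also infer that every access or mapping complication is lost. Only those that stop the case before insertion are. If the case goes on, the subject becomes ATTEMPT or TREATMENT and the event counts. The protocol does not fix when StablePoint goes in, and 10.6.2.1 lets it add geometry to the map. A stroke first found at the Day 1 to 7 NIHSS would not have stopped the procedure. This stands.

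**The size is assumed.** No section gives a frequency, and the top value of 1.0% is one fifth of the whole expected 5% event rate. The false-pass figures also hold only at the null. This stands, so the figures illustrate and do not estimate.

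**Counting from exposure to the test device is defensible.** The performance goal comes from a meta-analysis (11.1.1.2) whose component studies' safety-set rules are not shown. If those studies also counted from device insertion, a wider set here would be less comparable with the goal. The documents cannot settle this, and it justifies reporting both sets. It does not remove the mismatch with a composite that names procedure-related events.

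**The two start points differ.** Index procedure time is a duration measure and not a safety window, and 10.5.2 starts the study-related ablation procedure at transseptal access. This stands, so the fix has to name one start point.

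**Conclusion.** The point holds for one group: eligible subjects whose index procedure is stopped by a serious access, transseptal or Orion-mapping complication before StablePoint insertion, and in whom StablePoint is not later used. As written, their events enter neither primary safety endpoint. Measured against all started procedures, the direction is certain: the omission can only raise the event-free rate.

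The size is not known. One omitted event reverses either test at its pass limit. The rise in false-pass chance rests on three assumptions: 299 analysed subjects without censoring, a true rate exactly at the goal, and a frequency between 0.1% and 1.0%. The documents do not show that the safety result will be materially wrong, and at the planned event rate the effect is small. The change is worth making because the rule selects on outcome and the correction is cheap.

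**What to change.** - In 9.5.2 and Table 26-2, limit INTENT to subjects whose index procedure was not started.
- In 9.5.3 and Table 26-2, define ATTEMPT as eligible subjects whose index procedure started but who received no RF from StablePoint. They then receive the existing 30-day ATTEMPT follow-up and enter both safety analyses under 11.3.1. Those without events also join the denominator, so the rule does not depend on outcome.
- State one start point and reconcile first sheath (Table 26-2) with transseptal access (10.5.2). First sheath is needed to capture vascular access complications, which the composite counts.
- Report both safety endpoints on the device-inserted set as a sensitivity analysis, because the safety-set rules behind the performance goal are not shown.
- Say how an access complication is handled when ICE at the start of the procedure finds the subject ineligible. Under 9.5.1 such a subject is Consent Ineligible and outside the endpoints, and the wording above does not reach that case.

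**Cost.** Protocol wording, one classification rule in the data capture system, and 30-day follow-up for a few subjects. ATTEMPT subjects do not count toward the enrolment ceiling (9.5.3), so the sample size is unchanged. The observed safety rate may be slightly less favourable.
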